## [name]

recommendations are given in every case), training of CHWs and physician oversight of application treatment recommendations and CHW decisions regarding medication administration and referrals.

Exit criteria for the study includes the following:

- Patient with eGFR <30 mL/min will be unable to safely take metformin or glibenclamide and thus will be
  excluded from the program. These patients will be referred to San Lucas Mission Hospital (SLMH) for
  consultation with [name] regarding alternate medication therapy.

- Women who are found to be pregnant during the study
- Patients who require insulin or additional medication other than metformin or glibenclamide for diabetes control

Patients with mild adverse effects, such as gastrointestinal upset from metformin or mild hypoglycemia or hypoglycemia symptoms on glibenclamide will have their medication adjusted according to the titration algorithms used by the application. Patients who are unable to tolerate metformin or glibenclamide due to adverse effects will be referred to [name] for assessment and further treatment recommendations. Patients with more severe adverse effects, such as severe hypoglycemia (defined as resulting in alteration in mental status and requiring assistance from a CHW) or hypoglycemia not responsive to initial measures in the field will be transferred to SLMH via ambulance for further care.

The program will pay the costs related to ambulance transfer to SLMH and the cost of treatment for medication adverse effects. Patients may incur costs from treatment for other complications of diabetes that fall outside the scope of the program, though this care is highly subsidized through the SLMH.

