## 4.1.3 Primary Safety Endpoints

- Documented hypoglycemia (blood glucose <70 mg/dL)

- Hypoglycemia requiring emergency transport to the hospital and/or hospitalization
- Instances in which the application provided an incorrect recommendation
- Patient death

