The occurrence of documented hypoglycemia (including hypoglycemia requiring emergency transport to SLMH), hypoglycemia symptoms requiring the assistance of another person for treatment, signs of GI bleeding in patients taking aspirin, and other adverse effects reported by patients that are not consistent with GI side effects of metformin or mild hypoglycemia associated with glibenclamide (miscellaneous adverse effects) will be recorded through the smartphone application used for program execution and data entry. Treatment of hypoglycemia, including emergency transport if needed, will also be executed and recorded according to the hypoglycemia protocol (Appendix 4). Patients who require transport to SLMH will be assessed and treated by [name] and his staff, who will record treatments administered and patient outcomes, including need for hospitalization and any serious sequelae of the hypoglycemic event, including death. Patients taking aspirin who are experiencing possible GI bleeding will have their aspirin discontinued and will be referred to [name], who will record the results of any diagnostic evaluation and treatment required. Miscellaneous adverse effects of medications recorded by CHWs will be reviewed by [name] during his review of monthly patient visits (see section on "Physician supervision" in the Study Procedures section) and he will direct CHWs to take corrective action based on his clinical judgement.

Following each monthly visit, [name] will review treatment for all patients in the program. If the recommendations provided by the application and carried out by the CHWs goes against his clinical judgement, he will contact the CHW coordinators and direct them on corrective action. They will then visit the patient to follow up on their clinical status and carry out the actions recommended by [name]. When these corrective actions are necessary, [name] will communicate this to [name] and [name], who will record the reason that [name] disagreed with application recommendations and the corrective action that was recommended and carried out. Once per month, [name] will also review all treatment data to assess for compliance to program protocols, correctness of application treatment recommendations, and occurrence of adverse events. He will communicate his findings to [name] (PI), [name], [name], and the CHW coordinators in order to allow for corrective action and

Version #: 1.0

[name]

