## 10.6 Safety Oversight

[name] will review all patient data each month to identify patient safety issues. Any issues will be promptly discussed with site investigator and medical director, [name], and with the PI, [name]. Special attention will be given to the following potential safety issues:

- Documented hypoglycemia. This includes those episodes requiring emergency patient transport (severe) and non-severe (those treated without complication in the field). While this is a known but side effect of glibenclamide, frequent occurrences in our patients may suggest the need for an alteration in our medication titration protocols
- Severe probable hypoglycemia (patient reports hypoglycemia symptoms that required the assistance of another person to treat due to altered mental status)
- Incorrect recommendations regarding medication dosing, management of complications, or recommendations for referral provided by the application
- AEs and UPs as described above, which would also be reported to the IRB.

Interim cumulative safety analysis will occur at 3 months, 6 months, and 9 months and final safety analysis at 12 months.

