# Protocol for management of hypoglycemia detected with blood glucose testing during patient visit 1st glucose reading is <70

- Follow Up Question: "Is the patient unresponsive, very sleepy or confused "
  - YES: Unresponsive, very sleepy, or confused
    - Message: "Call a coordinator. The patient should be transported to the hospital immediately. The patient needs something with sugar (candy, juice, coke) immediately. If the patient is unable to drink something, sprinkle sugar under the tongue."
    - NO: Normal mental status
      - Message: "Blood sugar is low. Please re-test to confirm."
      - Re-test to confirm
- Promoter repeats blood glucose (reading 2)
  - Reading 2 ≥70
    - Message: "It is now in normal range. Continue with the questions."
  - Reading 2 <70

.

- Message: "It remains very low. The patient should eat something with sugar (candy, juice, coke) immediately". The app also provides a list of options for 15 grams of simple carbohydrate.
- Message: "Wait 15 minutes after eating and re-test."
- Re-test after eating and waiting 15 minutes
- Reading 2 ≥400
  - Message: "Drastic change. Please start over."
- Promoter repeats blood glucose (reading 3)
  - Reading 3 ≥70
    - Message: "It is now in a normal range. The patient should eat a full meal to prevent the blood sugar from dropping again. Continue with the questions after the patient has eaten."
    - Recommendation: "Be vigilant and seek medical attention if you begin to feel bad. You should have someone with you for the rest of the day"
    - Application will lower dosage of glibenclamide
    - Reading 3 <70
      - Message: "It remains very low. The patient should eat something with sugar (candy, juice, coke) immediately". The app also provides a list of options for 15 grams of simple carbohydrate.
      - Message: "Wait 15 minutes after eating and re-test."
      - Re-test after eating and waiting 15 minutes
- Promoter repeats blood glucose if indicated (reading 4)
  - Reading 3 ≥70

Version #: 1.0

.

<sup>14 Table sugar sprinkled under the tongue has been shown to be comparable to intravenous glucose for the treatment of severe hypoglycemia in two small studies performed in resource-limited settings

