#### [name]

- Message: "It is now in a normal range. The patient should eat a full meal to prevent the blood sugar from dropping again. Continue with the questions after the patient has eaten."
- Recommendation: "Be vigilant and seek medical attention if you begin to feel bad. You should have someone with you for the rest of the day. Do not take your glibenclamide today"
- Application will lower dosage of glibenclamide
- Reading 3 <70

  - Message: "It remains very low. The patient should eat something with sugar (candy, juice, coke) immediately if they are still alert and able to eat and drink. If they are not responding or very sleepy, sprinkle sugar under the tongue. Call the coordinator to arrange transport to the hospital for further treatment and monitoring"

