# Indications for referrals

- Routine referrals
  - Stage I hypertension (BP 140-160/90-100 mmHg)
  - Non-infected diabetic ulcer
  - Need for renal function testing
  - A1c ≥9 despite maximal doses of metformin and glibenclamide for ≥3 months
  - A1c ≥9 for 3 consecutive checks
  - A1c above glycemic target, but less than 9 for 4 consecutive checks
  - Recent chest pain, moderate risk (2 of 5 points)
  - Blood in stool or possible melena
  - $\circ$   $\;$  Patient has other symptoms not addressed by the program protocols
  - Urgent referrals
    - Stage II hypertension (BP 160-200/100-120 mmHg)
    - Possibly infected diabetic ulcer, no signs of systemic infection
    - Worsening vision
    - FBG detectable, but ≥400
    - o A1c ≥14
    - Patient cannot tolerate minimum doses of metformin and/or glibenclamide
    - Current chest pain, moderate risk (2 of 5 points)
  - Emergency referrals
    - Severe hypertension (BP ≥200/120 mmHg)
    - Fasting blood glucose undetectable high
    - Postprandial/random blood glucose undetectable high with mental status changes
    - Hypoglycemia associated with altered mental status
    - Persistent hypoglycemia despite treatment in the field
    - Current chest pain, high risk (≥3 of 5 points)
    - o Possibly infected diabetic ulcer with signs of systemic infection

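### Appendix 4: both branches of the fourth-glucose-reading step test reading 3, so as written reading 4 is never used and a recovered patient is sent to hospital

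*Combined protocol and SAP*

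**What the plan says.** Appendix 4 sets out what the community health worker (CHW) does when a first glucose reading at a visit is below 70 mg/dL. An alert patient is re-tested (reading 2). If still below 70, the patient takes sugar, waits 15 minutes and is tested again (reading 3). If reading 3 is also below 70, the sugar, wait and re-test are repeated. The next step is headed "Promoter repeats blood glucose if indicated (reading 4".

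Two branches sit under that heading:

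- The first is labelled Reading 3 ≥70. It says glucose is back in range, advises a full meal and vigilance, adds "Do not take your glibenclamide today", and has the application lower the glibenclamide dose.
- The second is labelled Reading 3 <70. It says glucose remains very low, repeats the sugar advice, and ends "Call the coordinator to arrange transport to the hospital for further treatment and monitoring".

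Other sections bear on this step:

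- Section 2.7.2 reserves ambulance transfer for patients with severe adverse effects such as severe hypoglycemia, or with "hypoglycemia not responsive to initial measures in the field will be transferred to SLMH via ambulance".
- Appendix 7 lists as an emergency referral "Persistent hypoglycemia despite treatment in the field".
- Section 10.3 makes Appendix 4 the operative text: "Treatment of hypoglycemia, including emergency transport if needed, will also be executed and recorded according to the hypoglycemia protocol".
- Section 4.1.3 has as a primary safety endpoint "Hypoglycemia requiring emergency transport to the hospital and/or hospitalization".
- Section 10.5 treats more than 3 severe episodes (documented glucose below 70 needing emergency transfer or hospitalization) as grounds for protocol review and for considering suspension.

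**The concern.** A step that exists to act on reading 4 should branch on reading 4. Here both conditions name reading 3, whose value has already been fixed as below 70 by the route into the step. Followed or coded literally, the fourth test is done and its result discarded.

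Three things would be at stake.

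- **Care.** A patient who responded to a second round of sugar would be told that glucose is still very low and would be sent to hospital. The advice to skip that day's glibenclamide, which Appendix 4 gives only in the unreachable branch, would never appear.
- **Safety counts.** Section 10.6 describes as "non-severe (those treated without complication in the field" the kind of episode this would be. If the patient were transported, it could instead be recorded under the transport endpoint and counted under section 10.5.
- **The reference standard.** Incorrect application recommendations are themselves a primary safety endpoint (4.1.3), and section 10.3 provides a monthly check of their correctness. If Appendix 4 is the yardstick, an application that rightly used reading 4 would depart from the text, and one that wrongly ignored it would agree with the text.

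**Working it through.** The plan gives no figure to reproduce. The check is of branching logic, using only the conditions in Appendix 4.

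**1. Entry condition.** The reading-4 step is reached only through the re-test instruction given when reading 3 is below 70. Inside the step, reading 3 <70 is therefore always true.

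**2. Branches as written.** Reading 3 ≥70 is always false there, so the recovery branch cannot be reached. Reading 3 <70 is always true, so every patient goes to transport.

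**3. Branches as evidently meant.** Reading 4 ≥70 leads to recovery; reading 4 <70 leads to transport.

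**4. Enumeration.** Take every whole-number pair of readings 3 and 4 from 40 to 120 mg/dL. That is 81 values each, of which 30 (40 to 69) are below 70 and 51 (70 to 120) are not.

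- Pairs that enter the step: 30 × 81 = 2,430.
- Of these, reading 4 ≥70: 30 × 51 = 1,530. Reading 4 <70: 30 × 30 = 900.
- As written: 0 of 2,430 go to recovery and 2,430 go to transport.
- Relabelled: 1,530 go to recovery and 900 go to transport.

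These counts show which routes can be reached. They are not probabilities.

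**5. End points after a first reading below 70.**

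| | Path | Intended | As written |
|---|---|---|---|
| 1 | Altered mental status | Transport | Transport |
| 2 | Alert, reading 2 70–399 | Continue | Continue |
| 3 | Alert, reading 2 ≥400 | Start over | Start over |
| 4 | Readings 1–2 <70, reading 3 ≥70 | Recovery | Recovery |
| 5 | Readings 1–3 <70, reading 4 ≥70 | Recovery | **Transport** |
| 6 | Readings 1–4 all <70 | Transport | Transport |

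The two versions differ on 1 of 6 end points, which is 1 of the 2 outcomes of the reading-4 step. Rows 2 and 3 resolve by intent an overlap in the text, where ≥70 and ≥400 are both listed under reading 2. Row 3 is a loop back to the start; leaving it out gives 1 of 5.

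**6. Is it a repeated block?** No. The branches under reading 4 contain the same-day glibenclamide hold and the hospital transport, and neither appears under reading 3. They are separate actions carrying the wrong label.

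**7. Comparison with the rest of the plan.** Row 5 as written sends to hospital a patient who did respond to field treatment. That contradicts the transfer rule in section 2.7.2 and the referral list in Appendix 7. Row 5 as intended agrees with both.

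**The case against.** The strongest reply is that this is a copying slip with only one sensible reading. The heading names reading 4, the messages make sense only for reading 4, and section 2.7.2 and Appendix 7 state the right rule. CHWs act on application messages, which carry no reading numbers. The application had already been tried with patients under physician supervision (2.1), and section 2.7.2 plans systematic testing of each scenario. In real time, the transport branch itself requires a call to the coordinator, CHWs may phone with questions, and for the first several months they are paired with a coordinator (7.4.1). A patient wrongly transported would be under physician care, and Appendix 10 also reduces glibenclamide after hypoglycemia. The link to section 10.5 needs several steps that nothing shows: the slip reaches the code, testing misses it, nobody intervenes, and an episode that did not really require transfer is still classed as severe.

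Most of this stands, and it is why the point is minor. The intent is clear, the direction is cautious, no fault in the application is shown, and the effect on safety counts is only a possibility.

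It does not make the text right. Section 2.3 says the programmed algorithms are those described in the protocol and its appendices, and section 10.3 makes Appendix 4 the rule to be carried out. Scenario testing needs a correct specification to test against. Physician review within a week of the visit (7.4.1) comes too late to prevent a same-day transport. Unlike Appendix 5 and the chest-pain protocol in Appendix 6, Appendix 4 also has no branch for a patient who declines transport. On the literal route, a recovered patient who refused would get no instruction from it to hold glibenclamide.

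**Conclusion.** The concern holds: the two branch labels under the reading-4 step are wrong as written. Literally applied, reading 4 has no effect, the recovery branch is unreachable, and 1 of 6 end points gets the wrong action. The error is over-referral; a patient still below 70 at reading 4 is sent to hospital under either version.

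Its size in practice cannot be stated, because the documents do not say how often three low readings are followed by a normal fourth. If such an episode were transported and classed as severe, it would add 1 to a trigger of more than 3, that is, one met at 4. That trigger prompts only review and consideration of suspension. No efficacy endpoint, test or sample size is touched.

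The conclusion about the text rests on Appendix 4 alone. Any consequence for patients or safety counts assumes that the labels were followed or coded literally, which the documents neither show nor exclude. Severity: minor.

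**What to change.** In Appendix 4, relabel the two conditions under the fourth-reading step Reading 4 ≥70 and Reading 4 <70.

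Then confirm in the application, with one case per branch, that both outcomes can be reached and depend on reading 4. For an alert patient:

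- Readings 65, 66, 64, 95 should give the recovery message with the advice to hold glibenclamide that day.
- Readings 65, 66, 64, 66 should give the transport message.

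The cost is two labels and two test cases within the scenario testing already planned in section 2.7.2. No extra visits, glucose tests or staff are needed.

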#### [name]

- Message: "It is now in a normal range. The patient should eat a full meal to prevent the blood sugar from dropping again. Continue with the questions after the patient has eaten."
- Recommendation: "Be vigilant and seek medical attention if you begin to feel bad. You should have someone with you for the rest of the day. Do not take your glibenclamide today"
- Application will lower dosage of glibenclamide
- Reading 3 <70

  - Message: "It remains very low. The patient should eat something with sugar (candy, juice, coke) immediately if they are still alert and able to eat and drink. If they are not responding or very sleepy, sprinkle sugar under the tongue. Call the coordinator to arrange transport to the hospital for further treatment and monitoring"

## **Appendix 5 - Hyperglycemia Protocols**

# Hyperglycemia

- 400≤FBG<HI
  - Urgent MD visit recommended in all cases
    - Patient willing to go
      - Dispense 5 days' worth of meds as a bridge based on 180(200)≤FBG<400 recommendations (if monthly visit) or A1c (month 3 or enrollment)
      - Arrange appointment
         Patient unwilling to go
        - Dispense medications based on 180(200)≤FBG<400 recommendations (if monthly visit) or A1c (month 3 or enrollment)
        - Follow up in 1-3 days
- FBG=HI

.

•

.

- Emergent visit recommended in all cases
  - Patient willing to  $go \rightarrow arrange emergency transport$
  - Patient not willing to go
    - Dispense medications based on 180(200)≤FBG<400 recommendations (if monthly visit) or A1c (month 3 or enrollment)
    - Follow up in 1 day
- PPBG=HI
  - "Is the patient unresponsive, very sleepy, or confused" (Y/N)
    - If YES, emergency visit recommended
      - Patient willing to  $go \rightarrow arrange emergency transport$
      - Patient not willing to go
        - Dispense medications based on 180(200)≤FBG<400 (if monthly visit) or A1c (month 3 or enrollment) recommendations
        - Follow up later that day or the next day
    - If NO
      - CHW advises patient to increase water intake
      - Dispense medications based on 180(200)≤FBG<400 recommendations (if monthly visit) or A1c (month 3 or enrollment)
      - Follow up with FBG in 1-3 days

Version #: 1.0

[name]

## **Diabetic Ulcers**

- Promoter asks patient: "Do you have wounds that won't heal on your legs or feet "
  - $\circ$   $\;$  If NO, application skips to the next topic in the visit
  - If YES, application initiates triage protocols as below
- Application prompts promoter to examine the patient's feet to assess for the following signs of infection:
  - Redness, warmth, swelling, and/or soreness of the skin around the ulcer
  - Copious or purulent secretions, foul odor
- If NO signs of infection, application recommends referral to doctor for routine visit sometime in the next 1-2 weeks
- If there are signs of infection, the following triage protocols are initiated:

 The ability to treat CAD and ACS in the San Lucas area is very limited. Chest pain is also a common symptom in primary care settings and is usually non-cardiac in origin. Thus, we tried to design an approach to possible symptoms of CAD/ACS in our relatively high-risk population that would detect patients with concerning presentations while at the same time limiting false positives, which could place a significant burden on the local health system. We have adopted a clinical prediction rule for identifying patients with chest pain who are at high risk of CAD. This rule relies on history alone and was validated in a primary care population

Version #: 1.0

#### [name]

- o Promoter prompted to check patient's oral temperature with digital thermometer
- Application reviews previously collected blood pressure and pulse (both obtained with automatic blood pressure cuff)
- If temperature >100.4 F (38 C) OR <96.8 F (36 C) OR pulse >90, OR systolic BP <90 mmHg → patient screens positive for possible systemic infection and/or sepsis, application prompts promoter to arrange immediate transport to the hospital
- If vitals do not screen positive for possible sepsis, the patient is referred to the doctor for an urgent appointment (within the next 1-2 days)

#### **Ophthalmic Complications**

- Promoter asks patient: "In the past month, have you had problems with your vision "
  - If NO, application skips to the next topic in the visit
  - If YES, application initiates triage questions as below
- Promoter asks patient: "Do these problems with your vision come and go, or are they constant "
  - If INTERMITTENT, application prompts promoter to advise patient that this is likely due to periods of high blood sugar and these vision problems should improve with better control of diabetes. Application then skips to next topic in the visit
- If CONSTANT, application continues triage questions as below
- Promoter asks patient "Has your vision worsened in the past month
  - If YES, application recommends urgent referral to doctor
  - o If NO, applications recommend that patients see doctor if having worsening vision problems

